#### **Duration of treatment**

Each subject will receive a single bolus *i.v.* injection of IMP or Placebo on study Day 1.

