#### 8.2.1 Secondary endpoints

The secondary evaluation parameters are:

- Change-from-baseline heart rate, PR and QRS interval ( $\Delta$ HR,  $\Delta$ PR and  $\Delta$ QRS)
- Categorical outliers for QTcF, HR, PR interval, QRS interval;
- Categorical analysis for T wave morphology;
- Relationship between Modufolin® plasma concentration and  $\Delta\Delta$ QTc
- Frequency, seriousness and intensity of AEs
- Physical examination
- Vital signs
- Safety laboratory measurements
- Plasma PK characteristics of Modufolin® for Injection, 100 mg and its metabolites:
  - [6R]-5,10- Methylene Tetrahydrofolate (MTHF; Modufolin® for Injection, 100 mg)
  - [6S]-5-Methyl-Tetrahydrofolate (5-Methyl-THF)
  - [6S]-Tetrahydrofolate (THF)
  - [6S]-5-Formyl-Tetrahydrofolic acid (5-Formyl-THF)

The PK parameters to be evaluated are listed in Section [17.7.5](#).

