### 17.7.5 Definition and calculation of folate pharmacokinetic parameters

The PK analysis will be based on the PPAS and subcontracted by the Sponsor to PKxpert. The PK parameters will be calculated by non-compartmental pharmacokinetic analysis (NCA) using the software Phoenix WinNonlin® version 6.4 or later (Pharsight Corporation, U.S.A.).

The following non-compartmental PK parameters will be assessed for [6R]-5,10-MTHF, [6S]-5-Methyl-THF, [6S]-THF and [6S]-5-Formyl-THF, if data permit:

**AUC** Area under the plasma concentration-time curve from time 0 to infinity. Calculated using the linear/log trapezoidal rule with extrapolation to infinity.

$$AUC(0 - t_{\max}) = \left( \sum_{i=1}^{n-1} \frac{C(i) + C(i+1)}{2} \cdot (t(i+1) - t(i)) \right)$$

The log trapezoidal rule is used from time  $t_{\max}$  to the last time point  $t$ :

$$AUC(t_{\max} - t) = \left( \sum_{i=1}^{n-1} \frac{C(i) - C(i+1)}{\ln\left(\frac{C(i)}{C(i+1)}\right)} \cdot (t(i+1) - t(i)) \right)$$

Extrapolation to infinity is performed using:

$$AUC(t - \infty) = \frac{C(t)}{\lambda_z}$$

$AUC_{\text{last}}$	Area under the plasma concentration-time curve from time 0 to the last time point $t$ .
$AUC_{\tau}$	Area under the plasma concentration-time curve in a dosing interval. Calculated using the linear/log trapezoidal rule with extrapolation to $\tau$ , if required
$AUC_{\% \text{Extrap}}$	Percentage of $AUC$ that is due to extrapolation from the last concentration to infinity:
	$AUC_{\% \text{Extrap}} = \frac{AUC(t - \infty)}{AUC} \cdot 100\%$
$AUMC$	Area under the first moment curve extrapolated to infinity based on the last observed concentration.
	$AUMC = AUMC_{\text{last}} + \frac{t_{\text{last}} \cdot C_{\text{last}}}{\lambda_z} + \frac{C_{\text{last}}}{\lambda_z^2}$
$C_0$	Back extrapolated concentration at time point 0 after intravenous administration
$C_{\max}$	Maximum plasma concentration
$C_{(\text{time})}$	Plasma concentration at a certain time
$C_{\text{ss}}$	Steady-state drug concentration in plasma
$CL$	Total body clearance for intravenous administration.
	$CL = \frac{\text{Dose}}{AUC}$
$LLOQ$	Lower Limit of Quantification
Mean	Arithmetic mean, otherwise specified
$MRT$	Mean Residence Time extrapolated to infinity.
	$MRT = \frac{AUMC}{AUC}$
$NCA$	Non-Compartmental pharmacokinetic Analysis
$PK$	Pharmacokinetics

Tau ( $\tau$ )	Dosing interval
$t_{\max}$	Time at which maximum plasma concentration is observed.
$t_{1/2}$	$t_{1/2} = \frac{\ln 2}{\lambda_z}$

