	Terminal half-life:
$\lambda_z$ ( lambda z )	Terminal rate constant. Calculated by log-linear regression of concentrations versus time
$V_z$	Volume of distribution based on the terminal phase.
	$V_z = \frac{\text{Dose}}{\text{AUC} \cdot \lambda_z}$
$V_{ss}$	Volume of distribution based at steady state.
	$V_{ss} = MRT \cdot CL$

Descriptive statistics for the PK parameters will be presented by treatment group with number of measurements, arithmetic mean, SD, Coefficient of variation (CV), median, minimum, maximum, geometric mean, geometric CV%.

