Absorption	Absolute/Relative Bioavailability  $T_{max}$	N/A, IV administration  
 
Median (range) for parent            N/A, IV administration
 
Median (range) for metabolites              [6S]-5-tetrahydrofolate ([6S]-THF): The concentration of the metabolite, THF, after IV administration of Modufolin® increased rather rapidly, <math>t_{max}</math> ranged between 5-15 min at 60 mg/m^2 and 15-45 min at 200 mg/m^2.              [6S]-5-Methyl-Tetrahydrofolate ([6S]-Methyl-THF):  <math>t_{max}</math> ranged between 1.5-4 h at 60 mg/m^2 and 3-6 h at 200 mg/m^2 
 

Distribution	Vd	The distribution volume ( $V_{ss}$ ) of MTHF was in the range of 9.2-22.7 L in the 60 mg/m  dose group and 9.4-29.3 L in the 200 mg/m  dose group.

	% bound	Not performed
Elimination	Route	
 
• Primary route; percent dose eliminated
 
 
IV. Not studied, but it is anticipated that most of the dose will enter the endogenous folate metabolism.
 
 
• Other routes
 
 
N/A

	Terminal $t_{1/2}$	
 
• Mean (<math>\pm</math> SD) for parent
 
 
The elimination half-life calculated for two patients in the high dose level (200 mg/m^2, measurable concentrations until 6 h) were 1.5-1.8 h, but the major part of the exposure of the parent compound was eliminated faster, a multi-compartmental elimination curve was seen for Modufolin® drug substance ([6R]-MTHF).
 
 
• Mean (<math>\pm</math> SD) for metabolites
 
 
[6S]-5-Tetrahydrofolate ([6S]-THF): one phase elimination curve with an elimination half-life less than 1.5 h
 
[6S]-5-Methyl-Tetrahydrofolate ([6S]-Methyl-THF): The concentration of methyl THF could be measured until 6 - 24 h. The PK of methyl THF for two patients at 200 mg/m^2 could be described by a one phase elimination curve with an elimination half-life of 4.3-14.5 h

	CL	The clearance (CL) of methylene THF, parent, was in the range of 31-60 L/h
Intrinsic Factors	Age	Currently no information available (popPK).
	Sex	Currently no information available (popPK).
	Race	Currently no information available (only caucasians studied hitherto).
	Hepatic & Renal Impairment	Currently no information available.
Extrinsic Factors	Drug interactions	Not performed

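### Section 17.7.5 applies the dose-based definitions of C0, CL, Vz and Vss to three metabolites that are never dosed, so for them CL and Vz are only apparent values, Vss is distorted and C0 has no meaning

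*Protocol*

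**What the plan says.** Protocol section 17.7.5 introduces its parameter list with "The following non-compartmental PK parameters will be assessed for" four analytes, namely MTHF, 5-methyl-THF, THF and 5-formyl-THF, subject only to the data permitting it. One list follows for all four analytes. The rows that matter here are:

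- C0: "Back extrapolated concentration at time point 0 after intravenous administration".
- CL: "Total body clearance for intravenous administration", with the formula Dose/AUC.
- Vz: "Volume of distribution based on the terminal phase", with the formula Dose/(AUC × λz).
- Vss, with the formula MRT × CL, where MRT = AUMC/AUC.

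No row is marked as parent only, and no apparent parameter or fraction-formed term is defined. The section ends by sending the PK parameters to descriptive tables by treatment group. The synopsis (Pharmacokinetic assessments) gives the same undivided list for the same analytes.

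On dosing, the synopsis says: "Each subject will receive a single bolus *i.v.* injection of IMP or Placebo on study Day 1". The injected substance is MTHF. Section 8.2.1 names the secondary endpoint as "Plasma PK characteristics of Modufolin® for Injection, 100 mg and its metabolites", so the other three analytes are products of the injected drug. On elimination of the parent, Appendix 18.3 says: "Not studied, but it is anticipated that most of the dose will enter the endogenous folate metabolism".

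**The concern.** CL, Vz and Vss each need to know how much of the measured substance entered the body. For MTHF this is the injected dose. For a metabolite it is the injected dose times the fraction converted, and the protocol has no value for that fraction. Followed literally, section 17.7.5 would put the MTHF dose into the numerator for each metabolite and print the result under the plain labels of clearance and volume of distribution.

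Such figures can look plausible, so a reader may not notice that they mix elimination with an unknown degree of formation. Section 9.2 says the PK data should support the design of further studies, which is where an unlabelled metabolite clearance or volume could be misread.

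**Working it through.** **1. The plan's own figure, for the parent.** Appendix 18.3 gives a clearance of 31-60 L/h for MTHF. It also gives average exposures of 2270 h·µg/L at 60 mg/m² (AUClast) and 7730 h·µg/L at 200 mg/m² (AUC0-2h). Body surface area is an assumption, 1.6-2.0 m²; section 10.4 sets only the upper limit of 2 m².

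- 60 mg/m²: 96 to 120 mg / 2.27 h·mg/L = 42 to 53 L/h.
- 200 mg/m²: 320 to 400 mg / 7.73 h·mg/L = 41 to 52 L/h.

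Both fall inside 31-60 L/h, so Dose/AUC behaves as expected for the injected substance. At 500 mg/m² the AUC0-4h of 13600 h·µg/L gives 800 to 1000 mg / 13.6 = 59 to 74 L/h, mostly above that range. Those data come from a different study and a truncated AUC, and they have no bearing on the point.

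**2. The formulas for a metabolite.** Mass balance, ignoring molecular-weight differences and back-conversion, gives

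AUCm = fm × Dose / CLm.

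Hence:

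- Dose/AUCm = CLm/fm.
- Dose/(AUCm × λz) = (CLm/λz)/fm, which is Vm/fm when λz reflects the metabolite's own elimination.
- MRTm = MRT of the parent + Vm/CLm (one-compartment case), so MRTm × Dose/AUCm carries the 1/fm factor and the parent's residence time.

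**3. Numerical check.** All values are assumed for illustration. The parent has dose 900 mg, CL 45 L/h and V 15 L, so its MRT is 15/45 = 0.33 h. The metabolite has true CL 10 L/h and V 20 L, so λz = 10/20 = 0.5 per h and its own residence time is 20/10 = 2.0 h. The metabolite MRT from AUMC/AUC is then 0.33 + 2.0 = 2.33 h.

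| fm | AUCm = fm × 900/10 (h·mg/L) | CL = 900/AUCm (L/h) | Vz = CL/0.5 (L) | Vss = 2.33 × CL (L) |
|---|---|---|---|---|
| 0.2 | 18 | 50 | 100 | 117 |
| 0.5 | 45 | 20 | 40 | 47 |
| 0.8 | 72 | 12.5 | 25 | 29 |
| 1.0 | 90 | 10 | 20 | 23 |
| True value | | 10 | 20 | 20 |

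CL and Vz are correct only at fm = 1. Vss is too high even then.

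**4. C0.** Back-extrapolation to time 0 presumes that the substance was placed in plasma at time 0. Appendix 18.3 reports tmax for 5-methyl-THF at 1.5-4 h (60 mg/m²) and 3-6 h (200 mg/m²), and for THF at 5-15 min and 15-45 min. These curves rise after dosing, so no injected starting concentration exists to recover.

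**5. Comparison with the sponsor's own summary.** Appendix 18.3 reports clearance for the parent only and Vss for MTHF only. For THF and 5-methyl-THF it gives concentrations, AUC, tmax and half-life. Section 17.7.5 does not carry that distinction over.

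**The case against.** The best defence is that the list is partly a glossary. It also contains LLOQ, Mean, NCA, PK and Tau, which nobody can assess for an analyte, so the opening sentence cannot commit the analyst to every row for every analyte. CL and C0 are worded for intravenous administration, which fits only MTHF, and Vss takes that limit over through CL. The qualifier about data permitting leaves room, a PK specialist runs the analysis, and Appendix 18.3 already reports CL and Vss for the parent alone. The SAP, which is not at hand, may sort this out.

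This makes it less likely that wrong figures would be reported, but it does not remove the defect. Vz has an explicit formula with no intravenous wording and no limit to the parent. The data qualifier concerns whether data suffice, and a metabolite AUC and λz may well suffice for the arithmetic. The protocol fixes analytes and formulas itself and then calls for summary tables.

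Three objections stand in full. No decision in the protocol uses a metabolite clearance or volume. Metabolite MRT can be computed without a dose, so it need not be removed. A metabolite-to-parent ratio would be an optional extra output.

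**Conclusion.** The point holds as a flaw in a secondary, descriptive analysis. For the three metabolites, the listed CL and Vz would be apparent values, inflated by 1/fm; Vss would be inflated by 1/fm and by the parent's residence time; C0 would have no interpretation. The size in this trial cannot be stated, because fm is not known.

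The example assumes one compartment each, no return of metabolite to parent, and metabolite elimination slower than the parent's. Appendix 18.3 notes that THF and 5-methyl-THF can be precursors of MTHF, so even CL/fm is an approximation.

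A reader might infer more than the documents support:

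- **That the Appendix 18.3 AUCs measure the error.** With the assumed body surface area, 800 to 1000 mg divided by the 500 mg/m² AUC0-4h gives 12 to 15 L/h for THF (AUC 66.7 h·mg/L) and 46 to 57 L/h for 5-methyl-THF (AUC 17.4 h·mg/L). These are illustrative only. The protocol's CL uses AUC to infinity, and 5-methyl-THF has a half-life of 4.3-14.5 h, so a 4 h window misses much of its exposure. There is also no true clearance to compare with.
- **That the cardiac conclusion is at risk.** It is not. Section 17.4.3 uses Modufolin concentrations and Modufolin Cmax.
- **That AUCτ and Css are an equal error.** They are template rows with no use after a single dose. Removing them is tidying.

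**What to change.** In section 17.7.5 and the synopsis list, mark C0, CL, Vz and Vss as applying to MTHF only. Alternatively, keep metabolite CL and Vz but label them as apparent (CL/fm, V/fm) with fraction formed unknown, and omit metabolite C0 and Vss.

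For the metabolites, keep AUC, AUClast, extrapolated percentage, Cmax, tmax, λz and t½. MRT may stay if it is described as including formation time. Delete AUCτ and Css while the list is open.

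The cost is a few words in two places. No sample, visit or analysis is added, and the result matches how Appendix 18.3 already reports CL and Vss.

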## 17.8 Statistical/analytical issues

### 17.8.1 Handling of dropouts or missing data

For information, refer to the SAP.

### 17.8.2 Interim analyses and data monitoring

Not applicable.

## 18 APPENDICES

[figure not shown]

## 18.2 Declaration of Helsinki

[http://www.up.ac.za/media/shared/Legacy/sitefiles/file/45/2875/declarationofhelsinki\\_fortaleza\\_brazil\\_2013.pdf](http://www.up.ac.za/media/shared/Legacy/sitefiles/file/45/2875/declarationofhelsinki_fortaleza_brazil_2013.pdf)

### 18.3 Summary of safety and pharmacokinetic data from Isofol Medical AB's previous clinical studies in cancer patients

Therapeutic dose	The ongoing clinical study ISO-CC-005 is investigating 60, 120 and 240 mg/m  . Based on current data the expected clinical dosing regimen in future clinical trials in metastatic colorectal cancer (lead indication) patients is 120 mg/m  Modufolin®.	
Maximum tolerated dose	
Doses of Modufolin® up to 500 mg/m^2/day has been administered to patients in study ISO-MC-091.
 
From animal studies:
 
In dogs, the 28-day toxicology studies indicate that doses of 200 mg/m^2 Modufolin® for Injection, 100 mg may be administered twice daily (i.e., total daily dose of 400 mg/m^2) resulting in safety ratios between dogs and humans above 10. Looking at the safety exposure margins for rats, the safety factors would still be above 10 even if 200 mg/m^2 doses were administered up to 6-8 times daily (i.e., total daily doses of 1,200-1,800 mg/m^2).
	
Principal adverse events	
Modufolin® alone is not anticipated to induce any AEs or DLTs. Modufolin® is a biomodulator of the 5-FU anticancer effect in colorectal cancer or as a rescue treatment after High Dose Methotrexate treatment.
 
In the ISO-CC-005 study in metastatic CRC patients (Modufolin® administered together with drugs such as 5-FU, irinotecan and oxaliplatin):
 
Most common AEs: nausea (25), diarrhea (24), fatigue (24) and vomiting (13).
 
Main DLT AE: Neutropenia (8)
	
Maximum dose tested	Single Dose	
In the ISO-CC-002 study, colorectal cancer patients have been exposed to single Modufolin® doses of 60 or 200 mg/m^2.
 
In the ISO-MC-091 study, rectal cancer patients have been exposed to single and multiple doses ranging between 10 and 500 mg/m^2/day.

Exposures Achieved at Maximum Tested Dose	Multiple Dose	
In the ISO-MC-091 study, rectal cancer patients have been exposed to multiple doses ranging between 10 and 500 mg/m^2/day.

	Single Dose	
Cycle 1 Day 15, 500 mg/m^2 n=6, (ISO-MC-091)
 
Modufolin® drug substance ([6R]-MTHF) (parent)  <math>C_{(10\text{min})} 23300 \pm 6680 \text{ ug/L}</math>  <math>AUC_{(0-4\text{h})} 13600 \pm 3430 \text{ h*ug/L}</math>
 
[6S]-5-tetrahydrofolate ([6S]-THF) Cycle 1 Day 15, 500 mg/m^2 (ISO-MC-091)  <math>C_{(10\text{min})} 30200 \pm 5780 \text{ ug/L}</math>  <math>AUC_{(0-4\text{h})} 66700 \pm 12900 \text{ h*ug/L}</math>
 
[6S]-5-methyl-tetrahydrofolate ([6S]-methyl-THF)  <math>C_{(10\text{min})} 1600 \pm 400 \text{ ug/L}</math>  <math>AUC_{(0-4\text{h})} 17400 \pm 3120 \text{ h*ug/L}</math>

	Multiple Dose	Cycle 3 Day 15, 500 mg/m^2 (ISO-MC-091) Modufolin® drug substance ([6R]-MTHF) (parent) $C_{(10\text{min})}$ 24200 ±2410 ug/L $AUC_{(0-4\text{h})}$ 14900 ±1450 h*ug/L  [6S]-5-Tetrahydrofolate ([6S]-THF) $C_{(10\text{min})}$ 31600 ±6330 ug/L $AUC_{(0-4\text{h})}$ 70800±12500 h*ug/L  [6S]-5-Methyl-Tetrahydrofolate ([6S]-Methyl-THF) $C_{(10\text{min})}$ 1400 ±420 ug/L $AUC_{(0-4\text{h})}$ 14900 ±4150 h*ug/L
Range of linear PK		60 and 200 mg/m  (ISO-CC-002) and 500 mg/m  (ISO-MC-091)  AUC last : Average values: 2270 h*ug/L at 60 mg/m  ( $t_{last}$ = 1-1.5 h, AUC 0-2h could not be calculated)  AUC 0-2h : Average values: 7730 h*ug/L at 200 mg/m  and 13200 h*ug/L at 500 mg/m  .  Thus, dose proportional increase was seen comparing 60 to 200 mg/m  , and a minor sub-proportional increase to dose increase was seen, comparing up to 500 mg/m  . It should be emphasized that 60 and 200 mg/m  was in one study with colon cancer patients (ISO-CC-002) and 500 mg/m  was in another study with rectal cancer (ISO-MC-091).
Accumulation at steady state		
 
Modufolin® drug substance ([6R]-MTHF) (parent, active metabolite), no accumulation after once daily dosing up to 500 mg/m^2/day.
 

Metabolites		Most relevant other metabolites:  [6S]-5-Tetrahydrofolate ([6S]-THF) and ([6S]-5-Methyl-Tetrahydrofolate ([6S]-Methyl-THF)  Both metabolites can serve as precursors to MTHF, but are not active in itself
Absorption	Absolute/Relative Bioavailability  $T_{max}$	N/A, IV administration  
 
Median (range) for parent            N/A, IV administration
 
Median (range) for metabolites              [6S]-5-tetrahydrofolate ([6S]-THF): The concentration of the metabolite, THF, after IV administration of Modufolin® increased rather rapidly, <math>t_{max}</math> ranged between 5-15 min at 60 mg/m^2 and 15-45 min at 200 mg/m^2.              [6S]-5-Methyl-Tetrahydrofolate ([6S]-Methyl-THF):  <math>t_{max}</math> ranged between 1.5-4 h at 60 mg/m^2 and 3-6 h at 200 mg/m^2 
 

Distribution	Vd	The distribution volume ( $V_{ss}$ ) of MTHF was in the range of 9.2-22.7 L in the 60 mg/m  dose group and 9.4-29.3 L in the 200 mg/m  dose group.

	% bound	Not performed
Elimination	Route	
 
• Primary route; percent dose eliminated
 
 
IV. Not studied, but it is anticipated that most of the dose will enter the endogenous folate metabolism.
 
 
• Other routes
 
 
N/A

	Terminal $t_{1/2}$	
 
• Mean (<math>\pm</math> SD) for parent
 
 
The elimination half-life calculated for two patients in the high dose level (200 mg/m^2, measurable concentrations until 6 h) were 1.5-1.8 h, but the major part of the exposure of the parent compound was eliminated faster, a multi-compartmental elimination curve was seen for Modufolin® drug substance ([6R]-MTHF).
 
 
• Mean (<math>\pm</math> SD) for metabolites
 
 
[6S]-5-Tetrahydrofolate ([6S]-THF): one phase elimination curve with an elimination half-life less than 1.5 h
 
[6S]-5-Methyl-Tetrahydrofolate ([6S]-Methyl-THF): The concentration of methyl THF could be measured until 6 - 24 h. The PK of methyl THF for two patients at 200 mg/m^2 could be described by a one phase elimination curve with an elimination half-life of 4.3-14.5 h

	CL	The clearance (CL) of methylene THF, parent, was in the range of 31-60 L/h
Intrinsic Factors	Age	Currently no information available (popPK).
	Sex	Currently no information available (popPK).
	Race	Currently no information available (only caucasians studied hitherto).
	Hepatic & Renal Impairment	Currently no information available.
Extrinsic Factors	Drug interactions	Not performed
	Food Effects	Intravenous administration / No food effects expected
Expected High Clinical Exposure Scenario		In the other investigated indication with the treatment of Modufolin® (Osteosarcoma), the drug candidate is used as rescue after High dose methotrexate administration. In scenarios of extreme Methotrexate levels, according to the Children's Oncology Group, doses of folic acids (e.g. Leucovorin/Calcium folinate) might be administered up to maximum 1500 mg q6h until Methotrexate levels are <0.1 $\mu$ M. This corresponds to a maximum dosage of 750 mg q6h Modufolin®. (Modufolin® is the active metabolite of Leucovorin/Calcium folinate, hence half the dosage is needed)

